## **2. Introduction**

### **2.1 Background & Aims**

Breast cancer is one of the most prevalent malignancies affecting women worldwide, and advances in treatment modalities such as surgery, chemotherapy, and radiation therapy have substantially improved survival rates. However, despite improved prognosis, many survivors experience persistent long-term physical and psychological complications following treatment. Reduced shoulder range of motion (ROM), cancer-related fatigue (CRF), and heightened stress levels are among the most commonly reported adverse outcomes. These complications are often the result of radiation-induced fibrosis, post-surgical scarring, muscular tightness, and systemic fatigue, with elevated cortisol levels serving as a physiological indicator of chronic stress. Collectively, these impairments negatively affect functional independence, limit participation in daily activities, and reduce overall quality of life among breast cancer survivors.

Exercise has emerged as a safe, effective, and non-pharmacological strategy to address many of these treatment-related sequelae. Multimodal exercise programs incorporating aerobic training, resistance exercises, flexibility training, and mind–body components have demonstrated beneficial effects on physical function, fatigue reduction, and stress modulation in cancer populations. Nevertheless, the effectiveness of these programs may vary depending on factors such as program delivery, patient engagement, and the quality of instruction provided during exercise sessions. Verbal cueing defined as structured linguistic instructions, motivational prompts, and corrective feedback delivered during exercise—has been shown in sports science and rehabilitation literature to enhance motor learning, improve biomechanical performance, increase adherence, and optimize exercise outcomes. By directing attention, reinforcing correct movement patterns, and promoting motivation, verbal cues may play a critical role in maximizing the therapeutic benefits of exercise interventions.

Despite the growing evidence supporting exercise-based rehabilitation, limited research has specifically examined the added value of verbal cueing in exercise programs for breast cancer survivors, particularly those undergoing radiation therapy. This period is often associated with heightened fatigue, increased stress, and progressive musculoskeletal impairments, including shoulder stiffness and reduced ROM. Radiation therapy, while essential for cancer control, can exacerbate joint pain, muscle tightness, and systemic exhaustion, thereby contributing to elevated cortisol levels that may further impair recovery and overall health. Although multimodal exercise interventions have shown promise in improving functional outcomes and regulating stress biomarkers in various clinical populations, their specific effects particularly when delivered with structured verbal cues remain insufficiently explored in radiation-treated breast cancer survivors.

The need for targeted and comprehensive rehabilitation strategies in this population is increasingly evident due to the rising global incidence of breast cancer and the growing number of long-term survivors. A high prevalence of shoulder dysfunction, upper limb impairment, postural abnormalities, pain, lymphedema, and reduced quality of life has been documented following multimodal cancer treatments. Moreover, there is limited emphasis on structured physiotherapy programs that simultaneously address shoulder function, cancer-related fatigue, and psychological stress, as well as a lack of evidence examining the combined effects of such interventions on functional, subjective, and physiological outcomes. Exercise-based rehabilitation and targeted physiotherapy represent cost-effective and accessible approaches to restoring shoulder mobility, reducing fatigue, and improving quality of life. The use of validated and objective outcome measures, such as active shoulder ROM and salivary cortisol levels, further strengthens the clinical relevance and translational significance of such interventions.

Accordingly, the aim of the present study is to evaluate the effectiveness of a multimodal exercise program delivered with and without verbal cues on shoulder range of motion, cancer-related fatigue, and cortisol levels in breast cancer survivors undergoing radiation therapy.

## **2.2 Background Literature Review**

Rao et al. (2025) described the anatomy and physiology of the human breast, explaining its complex structure and the changes it undergoes throughout life, from development in the womb to puberty, pregnancy, lactation, and menopause. The authors highlighted the importance of understanding breast components such as lobules, ducts, connective tissue, lymphatic drainage, and blood supply, as this knowledge is essential for accurate diagnosis, treatment planning, and effective management of breast diseases.

Xiong et al. (2025) discussed the diverse and heterogeneous nature of breast cancer, focusing on the role of genetic changes, molecular subtypes, and biological mechanisms in disease progression. Their review emphasized recent advances in precision medicine, including targeted therapies and AI-assisted diagnostic tools, which support personalized treatment approaches and improve long-term survivorship outcome.

Zhang et al. (2025) examined global breast cancer trends using GLOBOCAN 2022 data and reported that breast cancer is the most common cancer among women worldwide. The study highlighted major regional differences, with higher incidence rates in developed countries and higher mortality in developing regions, particularly South-Central Asia and India. These findings stress the need for better early detection, access to care, and comprehensive treatment strategies.

Gupta et al. (2025) showed that structured exercise programs significantly improve the quality of life of breast cancer patients and survivors. Their analysis demonstrated improvements in physical, emotional,

and functional well-being, emphasizing the importance of including exercise-based rehabilitation as part of routine survivorship care.

Murena et al. (2025) conducted a retrospective analysis of 67 breast cancer patients who underwent mastectomy followed by reconstruction and adjuvant therapy to examine scapular dyskinesis. A high prevalence was reported, with static dyskinesis in 64.2% and dynamic dyskinesis in 73.1% of patients, including notable bilateral involvement. The study found that surgical technique and rehabilitation exposure significantly influenced shoulder outcomes, with longer physiotherapy duration reducing the risk of dynamic dyskinesis and prepectoral reconstruction showing better scapular mechanics. These findings underscore the importance of early and sustained physiotherapy to prevent long-term shoulder dysfunction in breast cancer survivors.

### **3. Study Protocol**

#### **3.1 Research Design Outline**

The study was conducted as a completed clinical trial among breast cancer survivors undergoing radiation therapy at Saveetha Medical College and Hospital.

Initially titled “Impact of Verbal Cueing in Multimodal Exercise Rehabilitation: A Retrospective Study in Breast Cancer Survivors Undergoing Radiation Therapy,” the trial successfully evaluated the effectiveness of a multimodal exercise rehabilitation program delivered with verbal cueing compared to the same program delivered without verbal cueing.

Participants who were undergoing radiation therapy were allocated into two groups: one group received the multimodal exercise program accompanied by structured verbal cues, while the comparison group performed the same exercise program without verbal guidance. Upon completion of the intervention period, outcomes were assessed to determine the impact of verbal cueing on physical and physiological parameters.

The outcome measures included shoulder range of motion, cancer-related fatigue, and

physiological stress levels. Shoulder range of motion was measured using a universal goniometer for shoulder flexion, abduction, and external rotation. Cancer-related fatigue was evaluated using the FACIT–Fatigue scale, and physiological stress was assessed through salivary cortisol analysis.

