### **3.3 Recruitment**

All breast cancer survivors undergoing radiation therapy and attending the study setting were enrolled in the clinical trial after meeting the eligibility criteria. Participant information sheets and informed consent forms were provided to all eligible individuals, detailing the purpose of the study, intervention procedures, and inclusion and exclusion criteria. Participants who consented to participate were enrolled in the trial and underwent baseline assessments prior to the initiation of the intervention.

Baseline evaluations included assessment of shoulder range of motion using a universal goniometer, cancer-related fatigue assessment using the FACIT–Fatigue scale, and evaluation of physiological stress through salivary cortisol analysis. Written informed consent was obtained from all participants, and signed consent forms were collected and retained by the site principal investigator before the commencement of any study-related procedures.

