##### **4.2 Secondary outcome**

The secondary outcome measures were fatigue, assessed using the Functional Assessment of Chronic Illness Therapy–Fatigue (FACT-F) scale, and salivary cortisol levels, measured in ng/mL.

A total of 36 participants were included in the study and were equally allocated into two groups, with 18 participants in Group A and 18 participants in Group B. Descriptive statistics were expressed as mean  $\pm$  standard deviation (SD). Inferential statistical analysis will include tests of normality, homogeneity of variance, paired sample t-tests for within-group comparisons, and independent sample t-tests for between-group comparisons. The level of statistical significance was set at  $p < 0.05$ .

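### No random or concealed allocation is described, yet an unadjusted t-test is read as the effect of verbal cueing; adjust for baseline and state how the groups were formed

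*Combined protocol and SAP*

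**What the plan says.** On allocation, section 3.1 (Research Design Outline) has one clause: "Participants who were undergoing radiation therapy were allocated into two groups". Section 4.2 adds the numbers: "A total of 36 participants were included in the study and were equally allocated into two groups", 18 in each. Section 3.3 (Recruitment) covers eligibility, consent and baseline measurement but has no assignment step.

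On the type of study, section 3.1 opens with "The study was conducted as a completed clinical trial among breast cancer survivors". It then gives an initial title containing "A Retrospective Study in Breast Cancer Survivors Undergoing Radiation Therapy". Section 3.3 describes a prospective sequence: "Participants who consented to participate were enrolled in the trial and underwent baseline assessments prior to the initiation of the intervention".

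On analysis, section 4.2 plans checks of normality and of equal variance, paired t-tests within groups and independent-samples t-tests between groups, at a 0.05 level. It names no covariate and does not say whether post-intervention values or changes from baseline are compared. Section 3.3 shows that shoulder range of motion, FACIT-Fatigue and salivary cortisol were all measured at baseline.

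On interpretation, the aim in section 2.1 is to "evaluate the effectiveness of a multimodal exercise program delivered with and without verbal cues", and section 3.1 presents the outcome comparison as showing the impact of cueing.

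**The concern.** Both arms receive the same exercise programme and differ only in the cues. The contrast isolates cueing only if the groups are otherwise comparable. Random, concealed assignment would make them so on average, but the text describes neither. Without it, women who were fitter, more motivated or less fatigued could be over-represented in one arm.

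The documents name one plausible source of imbalance. Section 4 admits women still in radiotherapy as well as women who have recently finished it, and section 2.1 describes the radiotherapy period as one of greater fatigue, stress and shoulder stiffness. An uneven mix of the two could create a group difference with no help from cueing.

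The planned test does nothing about this, although the baseline data needed for adjustment were collected. At stake is whether a significant result can be attributed to cueing at all.

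**Working it through.** **The plan's own figure.** The sample size of 36 (18 + 18) comes with no effect size, SD or power, so there is no calculation to reproduce. For scale, a two-sided 5% t-test with 18 per arm has 80% power only for a difference of about 0.96 SD.

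**Inputs.** From section 4.2: n = 18 per arm (34 df) and a level of 0.05. Assumed, because the documents do not give them: a two-sided test, a true cueing effect of zero, a baseline difference D between groups (in SDs), and a baseline-to-post correlation r with equal SDs at both times.

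**Formulas.** With no true effect, the spurious group difference is:
- post-score t-test: r × D, with SD 1;
- change-score t-test: (r − 1) × D, with SD √(2(1 − r)).

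The false-positive rate is the rejection probability of a noncentral t with 34 df and noncentrality (difference ÷ SD) × √(18/2) = (difference ÷ SD) × 3.

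**Worked case, D = 0.5 and r = 0.7.**
- Post scores: 0.7 × 0.5 = 0.35 SD; noncentrality 1.05; rejection 17.5% (20,000 simulated trials: 17.8%).
- Change scores: −0.3 × 0.5 = −0.15; SD √0.6 = 0.775; ratio 0.194 in size; noncentrality 0.58; rejection 8.7% (simulation 8.6%). The bias now has the opposite sign: the group that starts better appears to improve less.

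**Range over the assumptions.**

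| D (SD) | r | Post-score test | Change-score test |
|---|---|---|---|
| 0.25 | 0.5 | 6.5% | 6.5% |
| 0.25 | 0.7 | 8.0% | 5.9% |
| 0.25 | 0.8 | 9.0% | 5.6% |
| 0.50 | 0.5 | 11.3% | 11.3% |
| 0.50 | 0.7 | 17.5% | 8.7% |
| 0.50 | 0.8 | 21.5% | 7.5% |
| 0.75 | 0.5 | 19.4% | 19.4% |
| 0.75 | 0.7 | 33.4% | 13.5% |
| 0.75 | 0.8 | 41.7% | 10.6% |

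**Sample size is not a cure.** At a constant spurious difference of 0.35 SD, the rate rises from 17.5% with 18 per arm to 41% with 50 and 69% with 100.

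**What adjustment does.** In this simple model, ANCOVA on the measured baseline removes the bias. It also helps if allocation was random: residual variance is 1 − r² = 0.51 at r = 0.7, against 1 for post scores and 2(1 − r) = 0.60 for change scores. It does not remove bias from unmeasured factors. A remaining bias of 0.3 SD of the quantity tested would still give about 14% false positives in a t-test of this size, and 0.5 SD about 31%.

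**The case against.** The strongest reply is that silence is not evidence of a bad procedure. Section 3.1 is headed as an outline, and nothing says that allocation was non-random. This stands. A reader might infer that staff chose who was cued; the documents do not show that, only that the method is undescribed.

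A reader might also take the retrospective title as proof that groups came from past care. The text does not support this either. The title is introduced as the initial one, sections 3.1 and 3.3 call the study a clinical trial, and 3.3 puts consent and baseline assessment before the intervention. What remains is a contradiction to be explained.

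Nor does the exact 18/18 split point to deliberate assignment. Under a fair coin its probability is C(36,18)/2^36 = 0.132, and it is the single most likely split.

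Finally, the false-positive rates rest on assumed imbalances, and a change-score test passes on less of a baseline imbalance than a post-score test when r exceeds 0.5. Both points are correct, so no particular inflation can be claimed for this trial. But section 4.2 does not say which score is tested, and neither version deals with unmeasured selection.

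**Conclusion.** The concern holds in this form: no random or concealed allocation is described, the design label is unreconciled, and an unadjusted comparison is given a causal reading while usable baseline data are left out of it. Any imbalance from selection can bias the result, and the documents do not allow its size to be estimated. With the assumed 0.5 SD imbalance and correlation 0.7, false positives are about 17.5% (post scores) or 8.7% (change scores) per outcome, against a nominal 5%. Over the assumed ranges the figures run from 6.5% to 42% and from 5.6% to 19%.

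If assignment was in fact random and concealed, documenting it settles the allocation point. The case for baseline adjustment and the need to explain the title would remain.

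**What to change.** 1. **Section 4.2.** Make the main between-group analysis a regression (ANCOVA) of the post-intervention value on group and the baseline value of the same outcome, whatever the allocation method. Add radiotherapy status at entry (still in treatment or recently finished) if it was recorded. If outcome data have already been examined, say that the model was changed afterwards.

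2. **Section 3.1.** State what actually happened: how, by whom and when participants were assigned, and whether the assignment was concealed until consent and baseline assessment were complete. The study is described as completed, so a randomisation procedure must not be written in unless it took place. If assignment was not random, call the study a non-randomised comparison, replace the effectiveness and impact wording in 2.1 and 3.1 with association, and note that unmeasured confounding remains.

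3. **Title.** Explain or remove the retrospective label so that 3.1 agrees with 3.3.

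The cost is one regression per outcome (three movements, fatigue and cortisol, so five models), some rewording, and possibly a weaker conclusion. The baseline values needed were already collected.

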## **Participants**

Breast cancer survivors undergoing radiation therapy from Saveetha medical college and hospital attended the study setting will be eligible to participate in this study.

### **3.3 Recruitment**

All breast cancer survivors undergoing radiation therapy and attending the study setting were enrolled in the clinical trial after meeting the eligibility criteria. Participant information sheets and informed consent forms were provided to all eligible individuals, detailing the purpose of the study, intervention procedures, and inclusion and exclusion criteria. Participants who consented to participate were enrolled in the trial and underwent baseline assessments prior to the initiation of the intervention.

Baseline evaluations included assessment of shoulder range of motion using a universal goniometer, cancer-related fatigue assessment using the FACIT–Fatigue scale, and evaluation of physiological stress through salivary cortisol analysis. Written informed consent was obtained from all participants, and signed consent forms were collected and retained by the site principal investigator before the commencement of any study-related procedures.

### **3.3 Administration**

**TABLE- 1(MMV protocol)**

Phase	Activities
1. Warm-Up	- Marching in place

(5 – 10 minutes)
	
 
- Arm swings and ankle pumps
 
- Neck and shoulder rolls
 

2. Aerobic exercise (15 – 20 minutes)
	
 
-Walking depending on progress and tolerance or
 
-Cycling
 

3. Resistance Training (15 – 20 minutes)
	
 
- Bodyweight (push-ups, squats, lunges)
 
- Resistance bands/light weights (bicep curls, shoulder press, leg extensions).
 
- Progression: Gradually increase reps, sets, or intensity as tolerated.
 

4. Flexibility and Stretching (5 to 10 minutes)
	
Static stretching: Shoulders, elbows, wrists, quadriceps, hamstrings, and calves.
 
Hold each stretch for 15-30 seconds.

5. Relaxation and Cool down (5 – 10 minutes)
	
 
- Deep breathing,
 
- Ankle pumps and
 
- Neck/ Shoulder rolls
 

## **Assessment & Outcomes Measures**

### **3.1.1 Primary outcomes**

#### **Shoulder Range of Motion (ROM)**

Shoulder range of motion was evaluated as a primary functional outcome measure, with particular emphasis on shoulder flexion, abduction, and external (lateral) rotation of the affected upper limb. These movements are critical for performing overhead activities, self-care tasks, and functional reaching, and are commonly restricted in breast cancer survivors due to radiation-induced fibrosis, post-surgical scarring, pain, and muscle tightness.

Active ROM was measured using a standard universal goniometer, following established anatomical landmarks and standardized testing positions to ensure accuracy and reproducibility. Assessments were conducted at baseline prior to the initiation of the exercise intervention and repeated at the end of the intervention period.

Improvements in shoulder flexion, abduction, and external rotation following the intervention indicate enhanced joint mobility, improved soft-tissue extensibility, and better functional use of the upper limb. Goniometric assessment of shoulder ROM is widely accepted in clinical and research settings and has demonstrated high intrarater and interrater reliability, making it a valid and responsive tool for evaluating changes in shoulder function in oncological rehabilitation populations.

### **3.1.2 Secondary outcomes**

Cancer-related fatigue was assessed using the Functional Assessment of Chronic Illness Therapy–Fatigue (FACIT–F) Scale, a validated, self-administered questionnaire specifically developed to evaluate fatigue

and its impact on daily functioning in individuals with chronic illnesses, including cancer. The FACIT–F consists of 13 items rated on a 5-point Likert scale ranging from 0 (“not at all”) to 4 (“very much”), with total scores ranging from 0 to 52.

- o Higher FACIT–F scores indicate lower levels of fatigue and better functional well-being. Participants completed the questionnaire at baseline and after completion of the intervention period.
- o Cancer-related fatigue is one of the most common and persistent symptoms experienced by breast cancer survivors undergoing radiation therapy and can markedly affect physical performance, emotional health, and overall quality of life. The FACIT–Fatigue Scale has demonstrated excellent reliability, validity, and sensitivity to change in oncology populations, making it an appropriate and responsive outcome measure for evaluating the effectiveness of exercise-based rehabilitation interventions.

### **Salivary Cortisol Level**

Physiological stress response was evaluated through the measurement of salivary cortisol levels, a non-invasive biomarker that reflects hypothalamic–pituitary–adrenal (HPA) axis activity. Saliva samples were collected under standardized conditions to minimize the effects of diurnal variation in cortisol secretion.

Samples were obtained at consistent times of the day at baseline and after completion of the intervention period to ensure comparability of results.

Elevated salivary cortisol levels are commonly associated with chronic stress, fatigue, and altered neuroendocrine regulation in breast cancer survivors undergoing radiation therapy. A reduction or normalization of cortisol levels following the intervention indicates improved stress regulation, enhanced autonomic balance, and better physiological adaptation to treatment-related stress.

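### The cortisol section reads a fall as better stress regulation and autonomic balance, but the planned comparison of means can show only lower cortisol unless baseline values are shown to be raised

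*Combined protocol and SAP*

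**What the plan says.** The Salivary Cortisol Level section describes cortisol as "a non-invasive biomarker that reflects hypothalamic–pituitary–adrenal (HPA) axis activity". It gives the reason for measuring it: "Elevated salivary cortisol levels are commonly associated with chronic stress, fatigue, and altered neuroendocrine regulation". The interpretation follows directly: "A reduction or normalization of cortisol levels following the intervention indicates improved stress regulation, enhanced autonomic balance". No reference range, cut-off, minimum change or clock time for sampling is given; samples are said only to be taken at consistent times of day.

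On entry, the Participants section names diagnosis, radiotherapy and site, and SAP section 4 adds an age range. Section 3.3 (Recruitment) says that patients "were enrolled in the clinical trial after meeting the eligibility criteria", but the available text does not itemise those criteria. It then says: "Participants who consented to participate were enrolled in the trial and underwent baseline assessments prior to the initiation of the intervention". Salivary cortisol is one of those baseline assessments.

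On analysis, SAP section 4.2 lists cortisol in ng/mL as a secondary outcome and plans mean and SD, with "paired sample t-tests for within-group comparisons, and independent sample t-tests for between-group comparisons". It does not say whether the independent test uses post-intervention values or changes. It plans no analysis of normalization, of women with raised baseline values, or with adjustment for baseline.

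**The concern.** The premise is about raised cortisol, but the interpretation that follows is not limited to raised cortisol. A reader who applies that sentence to the planned results would report a lower mean as improved stress regulation, whether or not there was raised cortisol to correct. Normalization is named as a sign of benefit but never measured. The autonomic inference has no measurement behind it at all.

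At stake is the wording of the trial's stress conclusion. Section 3.1 uses cortisol as the measure of physiological stress, and SAP section 4 names it in the primary objective although section 4.2 classes it as secondary.

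**Working it through.** The plan states no figure to reproduce here. The check sets the passages side by side and asks what the planned tests can show.

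**1. When do reduction and normalization agree?** Take a woman's baseline value against a laboratory range:

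| Baseline | A fall is | Normalization is |
|---|---|---|
| Above range | towards the range | a fall |
| Within range | not normalization | already met |
| Below range | away from the range | a rise |

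The two terms coincide only in the first row, which is the case that the section's premise covers.

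**2. Is the first row guaranteed by entry?** Not by any stated criterion. Participants, section 3.3 and SAP section 4 mention no cortisol level. Section 3.3 describes enrolment and then the baseline tests, so cortisol reads as a measurement and not as a screen. Section 2.1 says that radiotherapy can contribute to raised cortisol; that is a background expectation, not a description of these 36 women.

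**3. Can the planned tests supply the missing condition?** No. Add a constant c to every value:

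- Paired test: (post + c) − (baseline + c) = post − baseline.
- Independent test: (mean A + c) − (mean B + c) = mean A − mean B, with the SDs unchanged.

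A check on simulated data agreed. It used 18 per arm, baseline SD 1, mean change −1 in the cued arm and 0 in the other, and change SD 1. With all values moved by −3, 0 or +3 units, the cued-arm paired t was −7.60 each time, and the independent t on post values was −2.78 (p = 0.0087) each time. This is true of t-tests on any outcome and is not a fault in them. It shows that the step from lower to better must come from knowledge of the baseline level, which the plan does not call for.

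**4. Which comparison can carry a conclusion about cueing?** Suppose cortisol falls by d in both arms. Each within-group change is −d, and the between-arm difference is (−d) − (−d) = 0. Both paired tests could be significant and match the interpretive sentence, with no effect of cueing. Only the between-arm difference bears on the question.

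**5. Would restricting to women with raised baseline values solve it?** Not by itself. If baseline and post values have the same mean μ and SD, correlation ρ and a linear relation, a woman with baseline x has an expected change of −(1 − ρ)(x − μ) with no treatment effect. This is a fall whenever x > μ and ρ < 1. Selecting high baselines and then reporting falls would show regression to the mean as benefit.

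**6. Autonomic balance.** The section describes cortisol as an HPA-axis marker. The listed outcomes are shoulder range of motion, FACIT-Fatigue and cortisol, and none is an autonomic measure. This step needs no assumption about baseline values.

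**The case against.** The strongest reply is that the sentence is rationale, written in the same style as the remark in the range-of-motion section on what better movement indicates. It follows a sentence about raised cortisol and can be read with it. The SAP adopts no directional rule. The aims in section 2.1 and SAP section 4 concern cortisol levels, and a between-arm comparison of mean ng/mL answers that. Most of this stands: no planned test is wrong. It does not cover the autonomic inference, and it leaves the stress conclusion dependent on a condition that the plan neither states nor checks.

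Three stronger readings are tempting, and the documents support none of them.

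- A reader might infer that every fall is formally scored as benefit and every rise as harm. The SAP contains no such rule and gives no reading of a rise.
- A reader might infer that opposite movements, all of them normalization, would cancel in the mean. If a share p falls by d and 1 − p rises by d, the mean change is −pd + (1 − p)d = −(2p − 1)d, which is 0 at p = 0.5. The algebra is right, but it needs women below range, and nothing in the documents suggests that there are any. It also describes change within one group, not the contrast between arms.
- A reader might infer that entry certainly did not require raised cortisol. The criteria mentioned in section 3.3 are not itemised in the available text, so the safe statement is that no stated criterion requires it.

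**Conclusion.** The point holds as one of interpretation, and it is minor. The planned t-tests are valid comparisons of cortisol level. What they cannot support, without evidence that baseline values were generally raised, is the conclusion that stress regulation improved. They cannot support a conclusion on autonomic balance in any case.

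No numerical size can be given: the documents contain no reference range, baseline distribution or cortisol SD. The conclusion rests on two readings of the text: that no unlisted entry criterion concerns cortisol, which the order of enrolment and baseline testing makes likely, and that the interpretive sentence is meant to guide how the result is reported. If baseline values prove to be generally raised, a lower cued-arm mean could reasonably be described in the section's stress-regulation terms. The range-of-motion conclusion is unaffected.

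**What to change.** 1. Delete the inference about autonomic balance.
2. Reword the Salivary Cortisol Level section so that any cortisol conclusion rests on the between-arm difference, not on a fall within a group or in women selected for a high baseline. Preferably estimate that difference by ANCOVA: post-intervention cortisol on arm and baseline cortisol.
3. Report the baseline cortisol distribution by arm. If the laboratory's range for the collection time is available, also give the number above range at baseline and post-intervention in each arm, as description only. A full below/within/above cross-table would average 18/9 = 2 women per cell in each arm, too few for more than that.
4. Describe a lower cued-arm mean as lower cortisol. Call it improved stress regulation only if baseline values are shown to be generally raised.
5. Section 3.1 describes the trial as completed. If outcome data have been seen, label the added table and model post hoc.

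The cost is some rewording, one short table and one model, all from data already collected. The range for the collection time may not be obtainable, since no clock time is stated; the count above range would then be dropped. The downside is a weaker cortisol claim if baseline values were mostly not raised or cannot be classified.
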